The study is planned to be divided into four periods as illustrated in Figure 4. The only clinical measures to occur from the beginning of Period I are the StepWatch, Patient Journal, and Socket Comfort Score. After enrollment, the subject will spend 8 weeks (+/-2 weeks) using their own energy storage and return foot. Informed consent, demographic information, general health information, and adverse events will be collected during this period. After enrollment, the subject will be randomized to Revo, Taleo (if a transfemoral amputee), or the Proflex XC (if a transtibial amputee).

Period II – Period IV

Baseline measures are taken just prior to Period II. After the first 8 week follow up, the subject will crossover to the second comparator. After the second 8 week follow up, the subject will crossover to control. During Period IV, assessments will be repeated as in baseline. Table 2 summarizes the assessments and order of events.

[figure not shown]

Figure 4 Study Periods and Visits

Table 2 Assessments by Period and Study Visit

Period I (Control)			Period II (Revo/ Comparative)	Period III (Revo/ Comparative)	Period IV (Control)
	Visit 1	Visit 2	Visit 3	Visit 4	Visit 5
Measurement	Enrollment	Baseline 8 ± 2 weeks	Period II Follow up 8 ± 2 weeks	Period III Follow up 8 ± 2 weeks	Period IV Follow up 8 ± 2 weeks
Demographics / General Health	X				
SCS	X	X	X	X	X
ABC (extended)		X	X	X	X
PLUS-M		X	X	X	X
PROMIS-F (7a)		X	X	X	X
TAPES-FUN + TAPES-AR		X	X	X	X
EQ-5D-5L		X	X	X	X
6 Minute Walk Test (incl. BORG RPE and continuous HR)		X	X	X	X
Foot Preference Questionnaire					X
Patient Journal (incl. Pain Interference)	X	X	X	X	X
Step Count*	X	X	X	X	X
Adverse Events	X	X	X	X	X
Fitting with prosthetic foot for subsequent Period		X	X	X	

* Subject is fitted with StepWatch at previous visit so that the data may be collected prior to the following visit, this process starts at enrollment

Objectives

Safety

Safety Objectives

1. To characterize all device-related adverse events, stumbles, and falls experienced by subjects in the study by frequency and severity.

Effectiveness

Primary Efficacy Objectives

1. To characterize perception of mobility as measured by the PLUS-M while wearing the Revo-M compared to the everyday feet.
2. To characterize the level of activity restrictions as measured by the Trinity Amputation and Prosthesis Experience Scales Activity Restrictions subscale (TAPES-AR) while wearing the Revo-M compared to the everyday feet.

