The fittings during Period II and Period III are determined at random and according to amputation level. Subjects will be randomized to start with either the Revo (regardless of amputation level) or the comparative foot: Taleo if TF or KD, Proflex XC if TT. After completing Period II with the assigned foot, subjects will cross over to be fit with either the Revo, if starting with the comparative foot or the comparative foot if starting with the Revo.

Fitting process for the Revo-M investigational foot

The Revo prosthetic foot has several components which have different mechanical characteristics to allow the foot to be tailored to the patient. Subjects will complete several walking trials to determine the optimal configuration.

Fitting process for the comparative feet: Taleo and ProFlex XC

The Taleo is customizable with heel wedges that come in three different stiffnesses (soft, medium and hard). The CPO may give the subjects the opportunity to try each wedge to determine which is best.

ProFlex XC does not have any customizable components, so no configuration process is required.

Home-use Periods

Subjects will have four home-use periods during the study approximately 8 weeks in duration as shown in Figure 4 above. Prior to each home-use period, subjects will be fitted with the assigned foot and be given a Patient Journal and a StepWatch activity monitor. The Patient Journals will be completed weekly for the duration of the home-use period. The StepWatch will be worn for approximately one month and then mailed back to the clinical site. At the end of the home-use period, subjects will return to the site for a follow-up visit for assessments (see Clinical Tests & Measures for test descriptions).

Clinical Tests & Measures

Data collection for the following clinical functional assessments will be collected on eCRFs. Several questionnaires and two performance based measures will be used in the study.

For an overview of the assessments required by visit, see Table 2.

Activity monitoring (daily step counts)

The StepWatch will be used for activity monitoring to collect daily step counts during the first month of each home-use period.

Six-minute walk test (6minWT)

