All training will be documented using training records including the elements of training completed, the trainers that delivered the training and the signatures of the participants. Site initiation visits or conference calls may be made by a Sponsor-appointed Monitor to review the Study Protocol and documentation requirements with the Investigator and clinic support staff involved in the study. The Sponsor will then determine if additional center-specific training is needed and will ensure that all researchers involved in the project have adequate training. Study activities may only be performed once the Sponsor confirms activation of the investigational site.

In addition to training, at a minimum, the following documentation must be in place at the investigational site before patient enrollment begins:

- Current Investigator's and Sub-Investigator's CVs
- Signed study agreement
- Completed training in human research subject protection or an overview of Good Clinical Practice if required by the IRB.
- IRB approval letter for the Study Protocol and amendment(s)
- Patient Informed Consent approved by both the IRB and Otto Bock Healthcare Products GmbH

Adverse Events

Adverse Event Definition

An adverse event is any untoward medical occurrence in a patient. An underlying disease or symptoms associated with the underlying disease that were present prior to the fitting of study devices are not reportable. However, any increase in severity of the underlying disease or symptoms since a study fitting is to be reported as an adverse event. If an adverse event leads to multiple outcomes that sequentially worsen during the course of the study, the worst event is reported. For example, skin irritation leading to a wound infection would be reported as infection.

Adverse Event Reporting

Once a subject is enrolled, all adverse events must be reported until the subject is withdrawn or is terminated from the study.

Adverse Event Adjudication

Events will be adjudicated per the definitions below.

Serious Adverse Event

A Serious Adverse Event (SAE) is an Adverse Event that:

1. led to a death;
2. led to a serious deterioration in the health of the patient that
 - results in a life-threatening illness or injury;
 - results in a permanent impairment of a body structure or a body function;
 - requires hospitalization or prolongation of existing hospitalization;

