Data analysis will be primarily descriptive in nature. Categorical variables (such as gender) and ordinal variables (such as severity of adverse events) will be summarized by absolute and relative (percentages) frequencies. Continuous variables (such as age) will be summarized by the mean, median, standard deviation, minimum and maximum values observed. In addition, change in continuous measures of effectiveness (such as PLUS-M scores) will be evaluated by subtracting baseline from follow-up scores. The mean, median, standard deviation, minimum and maximum values observed will be used to summarize change scores. In addition, the significance of differences between baseline and follow-up scores may be tested using Wilcoxon's matched pairs signed ranks test. Two-tailed p-values ≤ 0.05 will indicate statistical significance. Each variable will be analyzed separately. For each variable analyzed, only subjects with valid values will be included in the analysis. A subject need not have valid values on all variables to be included in the analysis of any given variable.

Risk-Benefit Analysis

The potential risks and benefits of the Revo-M as well as the comparative devices, Taleo and ProFlex XC, are identified in the Instructions for Use.

Risks and Minimization of Risks

The Revo-M devices to be assessed in this study will have undergone thorough verification testing. The risk analysis for the Revo-M prosthetic foot resulted in a list of known or expected risks as shown in the table below. All were deemed "As Low As Reasonably Possible."

Risk	Potential harm		
	Injury	Function lost	Health hazard
Damage/ Break of load bearing parts	X		
Break of functionally relevant parts	X		
Failure of the guide elements for the tension element	X	X	
The connection to the prosthesis is lost	X		
Foot twists	X		
Damage to the product during manufacture or use	X		
Incorrect alignment	X		
Not compliance with the assembly guidelines	X		
Mechanical damage	X		
Mechanical damage of load bearing parts	X	X	

Risk	Potential harm		
	Injury	Function lost	Health hazard
Use not according to the MOBIS classification	X		
Use without foot cover	X		
Overload of the prosthesis caused by unsuitable combination of prosthetic components	X		
Weight limit is not specified or not readable	X		
Safety instructions are not sufficiently described			X
Use on more than one user	X	X	
Product is used too long	X		
Exceeding the time-stability of supporting structures	X		

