The following risk-minimizing measures will be taken:

- The subjects will be individually fit by an experienced CPO and instructed to report to the CPO all the problems with the prosthesis. The CPO will be trained by Ottobock in the handling of the new prosthetic foot.
- The first steps with the new prosthesis will be deliberately accompanied by exercises which accelerate adaptive behavior and train proper behavior in critical situations.
- The subjects will be instructed that in case of any technical issues concerning the prosthesis, they should stop using it until the issue is resolved and to contact the investigational site to schedule further steps.
- The participants will be informed that they should refrain from performing any activity if they do not feel confident or safe.
- All activities during in-clinic tests will be performed under the close supervision of qualified personnel.
- The Revo-M investigational device used in the study has passed a fatigue test for 750,000 gait cycles corresponding to approximately 9 months of use.

The risks to subjects inherent in study procedures are limited to those associated with the six-minute walk test. Complications associated with this test include excessive fatigue, angina, or light-headedness. Subjects' blood pressure and resting heart rate will be measured prior to the test in accordance with recommendations from the American Thoracic Society (ATS Statement, 2002). Subjects will be encouraged to stop during the test if needed to catch their breath, and the test may be stopped by the investigator if subjects exhibit symptoms listed above.

Benefits

Subjects may or may not experience benefits such as improved walking performance during the course of the study while wearing the study devices. In any case, all subjects will need to return the study devices at the end of the study and return to using their existing ESR feet. However, the study

results may help the Sponsor identify ways to improve future versions of the Revo-M. In addition, by characterizing the comparative safety and effectiveness of the Revo-M (relative to both existing ESR feet and the two comparative study feet), society, the O&P industry, and the Investigators may also benefit from the knowledge gained.

Study Management

Sponsor Responsibilities

Sponsor responsibilities include:

1. Ensuring the study is designed and managed in compliance with all appropriate regulatory standards and is conducted according to the Study Protocol.

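### The everyday foot is worn about twice as long as the Revo-M, but safety has no exposure denominator; if the two everyday-foot periods were pooled, raw event counts would favour the Revo-M

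*Combined protocol and SAP*

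**What the plan says.** **Exposure.** The Home-use Periods section states: "Subjects will have four home-use periods during the study approximately 8 weeks in duration". The Study Summary assigns them. For Period I, "After enrollment, the subject will spend 8 weeks (+/-2 weeks) using their own energy storage and return foot". The two study feet follow in randomized order: "After the first 8 week follow up, the subject will crossover to the second comparator". Then comes Period IV: "After the second 8 week follow up, the subject will crossover to control". Table 2 heads both Period I and Period IV as control and gives each follow-up a window of plus or minus 2 weeks.

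**Event collection.** Adverse Event Reporting states: "Once a subject is enrolled, all adverse events must be reported until the subject is withdrawn or is terminated from the study". Table 2 marks adverse events and the patient journal at all five visits. The Patient Journal section has subjects record falls in the weekly journal.

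**Objective and summary.** The safety objective is "To characterize all device-related adverse events, stumbles, and falls experienced by subjects in the study by frequency and severity". Data Analysis provides that "ordinal variables (such as severity of adverse events) will be summarized by absolute and relative (percentages) frequencies". It gives no rate per unit of time and no rule for tabulating safety by foot or by period.

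**Comparison promised.** The Benefits part of the Risk-Benefit Analysis speaks of "characterizing the comparative safety and effectiveness of the Revo-M (relative to both existing ESR feet and the two comparative study feet").

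**The concern.** Event counts, and the share of subjects with at least one event, grow with time at risk. The design gives the everyday foot two periods and the Revo-M one. A table with one column per foot would therefore show fewer falls on the Revo-M even if the weekly risk were identical. That artefact favours the investigational device, on the one comparison with everyday feet that the Benefits text says society and the industry will learn from.

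**Working it through.** The documents give no event rate, expected count or safety power, so there is no figure of the plan's own to reproduce. The rates below are assumptions, constant over time and equal on all feet.

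**Inputs from the documents**
- Everyday foot: 2 periods × 8 weeks = 16 weeks (window 12 to 20).
- Revo-M: 1 period × 8 weeks = 8 weeks (window 6 to 10).
- Comparative foot: 1 period, the same as the Revo-M.
- Minimum sample size: 24 (Sample Size section).

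**1. Count ratio under equal risk, everyday periods pooled**

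Ratio = Revo-M weeks / everyday-foot weeks.
- Nominal: 8/16 = 0.50.
- Window extremes: 6/20 = 0.30 and 10/12 = 0.83. As totals, these need every subject to sit at opposite limits.
- If an assumed 10% or 20% leave after the Revo-M period and before Period IV: 8/(8 + 8 × 0.9) = 0.53; 8/(8 + 8 × 0.8) = 0.56.

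**2. Percentage of subjects with at least one event**

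For r events per subject per 8 weeks (Poisson), the Revo-M percentage is 1 − exp(−r) and the pooled everyday-foot percentage is 1 − exp(−2r).

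| r (assumed) | Revo-M | Everyday foot | Ratio |
|---|---|---|---|
| 0.05 | 4.9% | 9.5% | 0.51 |
| 0.25 | 22.1% | 39.3% | 0.56 |
| 0.5 | 39.3% | 63.2% | 0.62 |
| 1 | 63.2% | 86.5% | 0.73 |
| 2 | 86.5% | 98.2% | 0.88 |

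The halving holds for counts and for rare events. It fades as events become common.

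**3. The same data with a denominator**

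With 24 completers, exposure is 24 × 16 = 384 subject-weeks on the everyday foot and 24 × 8 = 192 on the Revo-M. At r = 0.25, the expected counts are 24 × 0.50 = 12 and 24 × 0.25 = 6.
- Raw count ratio: 6/12 = 0.50.
- Rates: 12/384 = 3.125 and 6/192 = 3.125 per 100 subject-weeks, ratio 1.00.
- Revo-M against one everyday-foot period: 6 against 6, ratio 1.00.

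**4. Phase V**

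The Time Period section allows a further 6 months on the Revo-M. If those events were added (assumed 26 weeks, every subject continuing), Revo-M exposure is 8 + 26 = 34 weeks and the count ratio is 34/16 = 2.1. The artefact then runs against the Revo-M, so without a denominator even its direction depends on a data cut that the plan does not state.

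**5. What exposure does not change**

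The percentage of events falling in each severity grade does not depend on weeks worn. Nor is the contrast of the Revo-M with the Taleo or ProFlex XC distorted at nominal durations, since each is worn for one period.

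**The case against.** The strongest answer is that the plan never specifies the pooled table. The Data Analysis sentence is a general rule for categorical and ordinal variables, and its safety example is severity. Where the plan names the everyday foot in an efficacy analysis it says which measurement is meant: baseline for the primary tests, and end of Period I and end of Period IV for the exploratory ones. A table by period would fit the text and have about 8 weeks per column. This stands, so a reader who inferred that the stated summary itself makes the Revo-M look twice as safe would go beyond the documents. A table by period would not deliver the promised comparison either, because Periods II and III each mix Revo-M and comparative-foot wearers.

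A reader might also extend the halving to every kind of event. The documents do not support that:
- The objective concerns device-related adverse events, and the Relatedness section rates them to the study device or fitting procedure. The Clinical Study Summary lists the Revo-M, Taleo and ProFlex XC as study devices and the everyday foot as control. The everyday foot may have few such events by definition, however long it is worn.
- The Adverse Event Definition sets aside symptoms present before study-device fitting, which may thin out Period I reports.

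Finally, comparative safety appears only under Benefits. The safety objective is descriptive and carries no hypothesis. That limits the weight of the point but does not remove it: frequency is the primary safety objective, and frequencies on feet worn for different lengths of time cannot be read side by side without a denominator.

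**Conclusion.** The point holds in conditional form. It is established that nominal exposure is 16 against 8 weeks, that events are collected throughout, and that the plan offers only counts and percentages while promising comparative safety against existing feet.

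If safety is tabulated by foot with Periods I and IV combined, an equally safe Revo-M would show a count ratio of 0.50 for falls, stumbles and all-cause adverse events. The percentage of subjects affected would be lower by a factor between 0.51 and 0.88 over the assumed range of 0.05 to 2 events per 8 weeks. Both results assume a constant weekly risk, equal on all feet, and full follow-up.

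No direction of bias is established for device-related events.

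**What to change.** In Data Analysis, replace the bare count-and-percentage summary of safety with the following:
- Report falls, all-cause adverse events and, where recorded, stumbles by the foot worn at onset, as events per subject-week of actual wear, overall and by severity.
- Show the everyday foot separately for Period I and Period IV. Do not pool the two against a single Revo-M period in count or percentage tables.
- Keep any Phase V Revo-M events in a separate table with its own denominator.

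The cost is changed wording and table shells and slightly more analysis work; design and sample size stay as they are. The change assumes that onset dates and fitting dates are captured on the existing forms, whose fields the documents do not show. The Patient Journal section mentions falls but describes no recording of stumbles, so a stumble rate is possible only where stumbles are actually captured.
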